For the trial's secondary analyses, emergency room/hospital utilization and duration of cancer treatment will be compared between arms using stratified Fine-Gray competing risk regression with death as a competing event (stratified by cancer type, with robust sandwich covariance matrix estimates to account for site clustering). Physical function/health-related quality of life/symptom burden/financial burden as measured by the QLQ-C30 at 3 months and patient satisfaction/communication as measured by CAHPS items will each be compared between arms using a general linear mixed model approach including a fixed effect for cancer type, a random effect for site, and a continuous covariate for the corresponding baseline score. All other quantitative outcomes will be tabulated within arms descriptively (see below for separate description of qualitative analyses). While a focus of the non-survival assessments is the 3-month time point, analyses will include each post-baseline assessment time point (1, 6, 9, and 12 months) as well as longitudinal analyses incorporating all post-baseline PRO data. Supplemental analysis will also include multivariable analysis of each primary outcome including the following covariates: age (<60 versus \geq 60), gender (female versus male), race/ethnicity (white non-Hispanic versus other), education status (high school graduate/GED or less versus some college or more), disease type (e.g., gastrointestinal, genitourinary, gynecologic, breast, lung/head and neck, melanoma, versus other), prior computer/email/internet use (rarely or less versus sometimes or more), and oncology practice site location (predominantly urban/suburban vs rural). Subgroup analyses may also be conducted for each of these covariates. For patients who die, have missing data, or go off study before the time point of analysis, prior or off study data (whichever is later) may be carried forward. Similar to above, sensitivity analyses may be carried out with truncation of data at March 1, 2020, to assess for impact of COVID.

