## 2.6. Power

For overall survival, the trial’s initial sample size of 1,000 patients from 50 U.S. practices provided 80% power for a hazard ratio of 0.76 (based on the prior single-center randomized controlled trial) which is considered clinically meaningful (Sobrero AF, et al. 2015; Ellis LM, et al. 2014) using a two-sided alpha=0.05/2 log-rank test with 521 events observed during the observation period, computed using the formula by Xie and Waksman, 2003, with an intracluster correlation coefficient of 0.001 (estimated from the 10 largest legacy Alliance trials involving 12,717 total patients). This sample size also provided 95% power to measure the established clinically meaningful difference of 0.37 standard deviations on the QLQ-C30 Physical Function Scale based on a prior single-center randomized controlled trial (~9 points on the 100-point QLQ-C30 scale) between randomization groups using a two-sided alpha=0.05/2 t-test assuming an intracluster correlation coefficient of 0.055 (Adams G, et al. 2004), and assuming that 85% of patients are evaluable for the primary analysis at the 3-month time point.

In order to optimize power, the sample size was subsequently amended to 1,200 patients from 50 (+/-5) U.S. practices. Power for comparing physical functioning increased to 96-97% and power remained 80% for comparing overall survival under the assumption that statistical analysis would be conducted after 522 events. Each analysis would be undertaken with a two-sided alpha=0.05/2.

Finally, after an additional amendment to increase type I error for the overall survival analysis, with a total of 1,200 patients at 52 practices nationally, there was at least 90% power for a hazard ratio of 0.76 (based on the prior single-center randomized controlled trial) which is considered clinically meaningful using a two-sided alpha=0.05 log-rank test with 576 observed events, computed using the formula by Xie and Waksman, 2003, with an intracluster correlation coefficient of 0.001 (estimated from the 10 largest legacy Alliance trials involving 12,717 total patients). This power calculation further assumes drop-out of 150 patients in the first 2.5 years.

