#### 3.6.3. Analyses of secondary and exploratory endpoints

Mean change from baseline in physical function, symptom control, and HRQL at 3 months will be compared between arms using a linear combination of parameters from a general linear mixed model. Each model will include all available data from all time points (months 0, 1, 3, 6, 9, and 12). Fixed effects will include arm, time point, cancer type, and arm-by-time point interaction. A random practice intercept term will be included to account for clustering by practice. Repeated observations by patient will be modeled using compound symmetric correlation structure over time. Such values as the mean change from baseline at 3 months by arm, and difference in mean change from baseline at 3 months between arms will be estimated with confidence intervals based on the mixed model. Comparisons at other time points will also be carried out and graphically displayed using mean plots.

To supplement comparison of means, a responder analysis will also be employed. Patients who complete the QLQ-C30 at baseline and at 3 months will be categorized as improving on each outcome (physical function, symptom control, HRQL) if their score increased by 5 or more points from baseline; worsening if their score decrease by 5 or more points from baseline; and otherwise as stable. The selection of a 5-point change on the 100-point QLQ-C30 scale was selected as clinically meaningful based on work by Cocks K, et al. 2012. The proportion of patients with improvement, stability, or worsening will be compared between arms at 3 months using a cumulative logistic regression model with fixed effects for arm and cancer type and a random practice intercept term to account for clustering by practice.

Similar to the mean comparisons, the responder analysis will be carried out at other time points as needed to supplement that primary analysis at 3 months.

See Section 3.5.3 for statistical analysis combining physical function, symptom control, and HRQL with overall survival data to be conducted at time of overall survival analysis.

Patient adherence (feasibility) to the intervention (i.e., completion of the weekly symptom surveys) is defined at each week as the proportion of participating patients completing a survey divided by the number of participating patients who are expected to complete a survey. Completion will be computed at each week and overall.

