### 3.6.4. Sensitivity analyses for secondary endpoints

As described above, supplemental analyses will include mean and responder comparisons at time points other than 3 months. For the responder analysis, a 10-point change will also be applied to ensure results remain consistent with a higher threshold. Finally, impact of the COVID pandemic will be explored by repeating key between-arm analyses within the subset of patients enrolled prior to December 1, 2019 (date selected to ensure that the 3-month time point occurred prior to widespread COVID pandemic impacts on clinical practices in the US). Outcomes of patients enrolled after December 1, 2019, may also be tabulated and compared to outcomes of patients enrolled prior to December 1, 2019.

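### The random practice intercept in SAP 3.6.3 cancels from the month-3 change contrast, so the QLQ-C30 mean-change intervals make essentially no allowance for practices differing in change, and SAP Section 4 does not declare the departure from the protocol's 3-month model

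*SAP*

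**What the plan says.** SAP 3.6.3 compares arms on mean change at 3 months in physical function (the key secondary endpoint), symptom control and HRQL.

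- Baseline is part of the outcome vector: "Each model will include all available data from all time points (months 0, 1, 3, 6, 9, and 12").
- Fixed effects are arm, time point, cancer type and arm-by-time. Repeated observations within a patient have compound symmetry.
- The practice-level term is a single intercept: "A random practice intercept term will be included to account for clustering by practice". No practice-by-time effect and no sandwich variance is stated for this model.
- The effect and its interval come from the model: "difference in mean change from baseline at 3 months between arms will be estimated with confidence intervals based on the mixed model".

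The same approach carries over to the other QLQ-C30 scales (3.6.3) and to the models fitted within each subgroup level (3.8).

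Protocol 7.1 specifies a different 3-month comparison: the 3-month score is modelled with cancer type, "a random effect for site, and a continuous covariate for the corresponding baseline score". It also plans longitudinal analyses, but of post-baseline data. SAP Section 4 declares changes to the subgroups and to the primary survival analysis only.

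**The concern.** The SAP says that the practice intercept accounts for clustering. For a difference between two visits it cannot do so, because a practice's intercept is the same at month 0 and month 3 and drops out. If practices differ in how much their patients change, that variation is missing from the interval.

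Such differences are plausible. The intervention is delivered at practice level and depends on local staff forwarding and acting on alerts (protocol 5.4.3 and 5.4.4). Protocol 7.1 sets no significance threshold for success, so the width of the interval matters to interpretation, and a reader would take the stated practice term as having dealt with clustering.

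**Working it through.** **1. The plan's own figure.** SAP 2.6 powers the 3-month physical-function comparison on 0.37 SD (about 9 points), two-sided alpha 0.05/2 and 85% evaluable, "assuming an intracluster correlation coefficient of 0.055". With m evaluable patients per practice, the design effect is 1 + (m − 1) × 0.055, and the evaluable number per arm is divided by it.

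- 1,000 patients in 50 practices: m = 850/50 = 17, design effect 1.88, power 95.5% (stated 95%).
- 1,200 patients in 45, 50 and 55 practices: design effect 2.19, 2.07 and 1.97, power 96.0, 96.9 and 97.6% (stated 96-97%).
- With no design effect, power is 99.9% or more in both cases.

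The figures reproduce, and the planning did carry a practice allowance.

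**2. Cancellation.** Write a patient's score in practice j at time t as fixed effects + b_j + patient effect + error. The contrast is (month 3 − month 0) in one arm minus the same in the other. b_j enters with +1 and −1 and disappears. A generalised least squares check (52 practices of 23 patients, compound symmetry with an assumed within-patient correlation of 0.6) gives these standard errors in SD units:

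| Practice-intercept variance | 0 | 0.055 | 0.15 | 0.30 |
|---|---|---|---|---|
| Complete data | 0.05173 | 0.05173 | 0.05173 | 0.05173 |
| Dropout (85% at month 3, 50% at month 12; assumed) | 0.0551 | 0.0551 | 0.0551 | 0.0551 |

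With unequal practice sizes as well, the change stays below 0.1%.

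**3. What is left out.** Take 52 practices and 1,200 × 0.85 = 1,020 evaluable patients, so m = 19.6. If the ICC of change is ρ, the true variance is the model variance times 1 + (m − 1)ρ, and

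size = 2 × [1 − Φ(1.96 × k / √(1 + (m − 1)ρ))],

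where k is the model SE divided by the SE that is correct when ρ = 0. If compound symmetry fits, k = 1. The documents give no ρ, so the range is assumed.

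| ρ | 0 | 0.01 | 0.02 | 0.055 |
|---|---|---|---|---|
| √(1 + (m − 1)ρ) | 1.00 | 1.09 | 1.17 | 1.42 |
| Size at nominal 5%, k = 1 | 5.0% | 7.2% | 9.4% | 16.8% |
| Coverage of 95% interval, k = 1 | 95.0% | 92.8% | 90.6% | 83.2% |

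**4. In points.** SD = 9/0.37 = 24.3. With a within-patient correlation of 0.6 (assumed), SD of change = 24.3 × √(2 × 0.4) = 21.8, and the model SE = 21.8 × √(4/1,020) = 1.36. At ρ = 0.02 the true SD is 1.36 × 1.17 = 1.60. The half-width is 2.7 points where 3.1 is needed (3.2 with t on 50 df).

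**5. Factors that move this.**

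- *Compound symmetry overstates the SE.* Under exponential correlation decay with the same dropout, k = 1.17-1.25. Size is then 2.4-3.5% at 0.01, 3.6-5.0% at 0.02 and 8.5-10.7% at 0.055. Mild decay gives k = 1.02-1.07, and 7.3-8.8% at 0.02.
- *Compound symmetry understates the SE.* If baseline correlates less with later visits than they do with each other, k = 0.88-0.94, and size at 0.02 is 11.6-14.1%.
- *Only intervention practices vary* (k = 1; the practice term is halved): 6.1, 7.2 and 11.1% at 0.01, 0.02 and 0.055.
- *Unequal practice sizes* (assumed CV 0.64, m replaced by m(1 + CV²)): 8.2, 11.3 and 21.2%.

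**6. Simulation.** 4,000 runs per cell, 52 equal practices, the same dropout, a practice level variance of 0.055 of the total, and a REML fit of the SAP model with cancer type omitted. Size at nominal 5%:

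| ρ | 0 | 0.01 | 0.02 | 0.055 |
|---|---|---|---|---|
| SAP model | 4.6% | 7.8% | 10.5% | 18.3% |
| Practice-clustered variance, 50 df | 5.1% | 5.2% | 5.2% | 4.5% |
| Protocol 7.1 model, month-3 completers | 4.9% | 4.9% | 4.9% | 5.0% |

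Monte Carlo error is about 0.35 points near 5% and 0.5 near 10%. Compound symmetry is close to correct here (mean SE 1.339 against true SD 1.335 at ρ = 0), so these runs do not test the misfit in step 5.

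**The case against.** The strongest reply is that the cancellation is certain but its consequence is not.

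- **The size rests on a quantity that the documents do not give.** A reader might take 0.055 from SAP 2.6 as the ICC of change and conclude that the analysis omits a design effect near 2. The SAP does not identify it so; it is a planning value for a 3-month t-test. With a level ICC of 0.055 and a within-patient correlation of 0.6, an ICC of change of 0.055 needs practice effects to correlate only 0.6 between baseline and month 3; 0.02 needs about 0.85. The top of the range is weakly supported. This stands.
- **Correlation decay alone can remove the inflation** at 0.01 and 0.02 (step 5). This stands, although misfit in the other direction adds to it.
- **Other analyses allow practices to differ in change.** The responder model has "fixed effects for arm and cancer type and a random practice intercept term to account for clustering by practice" applied to change categories, and "For the responder analysis, a 10-point change will also be applied to ensure results remain consistent with a higher threshold". Protocol 7.1 bases interpretation on all conducted analyses, so one interval does not decide the trial. This stands, but the responder analyses use categories among completers and do not correct the mean-change interval.
- **A repeated-measures model was foreseen.** A reader might infer that the SAP introduced longitudinal modelling without notice. Protocol 7.1 plans longitudinal analyses of post-baseline data. What is undeclared is narrower: a change contrast with baseline as an outcome serves as the main 3-month comparison.
- **The practical effect is modest over much of the range.** At 0.02 the half-width goes from 2.7 to 3.2 points, against a responder threshold of 5 and a design difference of about 9, on a secondary endpoint. This limits the severity; it does not make the stated practice term do its job.

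**Conclusion.** The point holds in a limited form and should be fixed. The cancellation follows from the model as written and needs no assumption about the data. Whether the interval undercovers depends on how far practices differ in change and on how well compound symmetry fits, and the documents settle neither. If compound symmetry fits, coverage falls from 95.0% to 90.6% at an assumed ICC of change of 0.02; at an ICC of 0 there is no loss.

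A reader might infer that the key secondary result is wrong or its interval shown to be too narrow. The documents do not support that: undercoverage is possible, not established. The point covers the mean-change models for physical function, symptom control, HRQL and the other QLQ-C30 scales, and the within-level models of SAP 3.8. It does not extend to the survival analysis, the responder analyses or the arm-by-subgroup interaction tests.

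**What to change.** - **SAP 3.6.3:** keep the longitudinal point estimate and all available data, as SAP 3.1.4 intends. Base the interval on a practice-clustered, small-sample-corrected variance, using t with contributing practices minus 2 df (about 50 for 52 practices), or on an equivalent practice-by-time random effect.
- **Supporting analysis:** report the protocol 7.1 model (month-3 score on arm, cancer type and baseline score, with a random practice effect). State that nothing is carried forward, because protocol 7.1 says that "prior or off study data (whichever is later) may be carried forward".
- **Scope:** do the same for the other QLQ-C30 scales and the within-level models of 3.8. Take care where a level holds few practices, such as rural, because the clustered variance was checked only with 52.
- **SAP Section 4:** declare the change from the protocol's 3-month model.
- **Labelling:** SAP 3.5.3 places the secondary analyses before the survival analysis and Section 5 lists their publication, so show this as a labelled re-analysis beside the original result.

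The cost is a small re-analysis of existing data and a few sentences. If compound symmetry fits, intervals widen by about 2% at an ICC of change of 0 (2.009/1.96) and about 20% at 0.02 (1.17 × 2.009/1.96; 21% in simulation). If it overstates the SE they change less or narrow: with k = 1.17-1.25, dividing those ratios by k gives intervals 12-18% narrower at 0, and between 4% narrower and 3% wider at 0.02.

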### 3.6. Secondary and exploratory endpoint evaluation

#### 3.6.1. Secondary and exploratory endpoints

As described above, the key secondary endpoint is physical function at 3 months as measured by the EORTC QLQ-C30 Physical Function Scale. Additional secondary endpoints include: EORTC QLQ-C30 symptom burden (control) score at 3 months, and EORTC QLQ-C30 HRQL score at 3 months.

Additional endpoints include: EORTC QLQ-C30 appetite loss, constipation, diarrhea, dyspnea, fatigue, insomnia, nausea/vomiting, and pain score at 3 months; EORTC QLQ-C30 function scales at 3 months, patient adherence to the intervention (i.e., completion of the weekly symptom surveys); CAHPS item scores at 3 months; emergency room visits; alert notification; and financial toxicity.

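### The compound symmetric covariance fixed for the QLQ-C30 models is unchecked; if correlation falls with time, the 3-month interval is too wide and the month 9 and 12 intervals too narrow

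*SAP*

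**What the plan says.** SAP 3.6.3 sets the target: "Mean change from baseline in physical function, symptom control, and HRQL at 3 months will be compared between arms". The data are pooled over visits: "Each model will include all available data from all time points (months 0, 1, 3, 6, 9, and 12". Two terms describe the dependence. For practices: "A random practice intercept term will be included to account for clustering by practice". For patients: "Repeated observations by patient will be modeled using compound symmetric correlation structure over time". The 3-month means and the difference between arms are to be "estimated with confidence intervals based on the mixed model". Later visits are also tested: "Comparisons at other time points will also be carried out and graphically displayed using mean plots".

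SAP 3.8 specifies the same covariance for subgroup models. SAP 3.6.3 extends similar models to the other QLQ-C30 scales.

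On status, SAP 3.6.1 says that "the key secondary endpoint is physical function at 3 months as measured by the EORTC QLQ-C30 Physical Function Scale". SAP 3.5.1 records that it was one of two primary endpoints at activation.

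Neither document names another covariance, a fallback or a robust standard error for these models. SAP 3.6.4 varies the time point, the responder threshold and the COVID period. SAP 3.1.4 offers multiple imputation if selection bias is a concern. Protocol 7.1 describes a model with "a random effect for site, and a continuous covariate for the corresponding baseline score" and states no repeated-measures covariance; its sandwich estimates apply to survival and competing-risk analyses only.

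**The concern.** Compound symmetry assumes the same variance at every visit and the same correlation for every pair, whether 1 or 12 months apart. In metastatic disease, scores close in time are likely to be more alike than scores a year apart. A single pooled correlation then misstates the precision of contrasts whose separation is far from the average. Because the intervals come from the model, nothing in the plan would correct or reveal this.

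Two things are at stake. At 3 months, an interval that is too wide costs power on the key secondary endpoint. At months 9 and 12, intervals that are too narrow overstate the evidence for or against a lasting effect. Protocol 7.1 sets no significance threshold and rests interpretation on all analyses together, so interval widths at every visit carry weight.

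**Working it through.** **1. The plan's own figure.** SAP 2.6 gives 95% power for 0.37 SD in physical function, with two-sided alpha 0.025, ICC 0.055, 85% evaluable, 1,000 patients and 50 practices.

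- Evaluable patients per practice: 1,000 × 0.85 / 50 = 17.
- Design effect: 1 + 16 × 0.055 = 1.88.
- Effective patients per arm: 425 / 1.88 = 226.
- Power: Φ(0.37 × √(226/2) − 2.241) = Φ(1.69) = 95.5%.

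With 1,200 patients, the same steps give 96.0%, 96.9% and 97.6% for 45, 50 and 55 practices, against a stated 96-97%. Both figures reproduce. They rest on a t-test, so the repeated-measures covariance does not enter them.

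**2. What compound symmetry pools.** Visits at months 0, 1, 3, 6, 9 and 12 form 15 pairs, with separations 1, 2, 3, 3, 3, 3, 5, 6, 6, 6, 8, 9, 9, 11 and 12 months. The sum is 87 and the mean 87/15 = 5.8 months. The key contrast spans 3 months and the last spans 12.

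**3. Standard error ratio.** With complete data and equal variances, a constant practice intercept cancels from the change score. For the change from baseline to month t:

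- true variance is proportional to 2(1 − ρ(t));
- model variance is proportional to 2(1 − ρ̄), where ρ̄ is the mean over the 15 pairs;
- ratio of model to true SE = √[(1 − ρ̄)/(1 − ρ(t))].

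**4. Assumed correlations.** The documents give none. The assumption is 0.70-0.85 at 1 month falling to 0.40-0.60 at 12 months. For linear decline from a to b, ρ(t) = a − (a − b)(t − 1)/11, so ρ̄ = a − (a − b) × 4.8/11.

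Middle case, 0.80 to 0.50:

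- ρ̄ = 0.80 − 0.30 × 4.8/11 = 0.669
- ρ(3) = 0.80 − 0.30 × 2/11 = 0.745; ratio √(0.331/0.255) = 1.14
- ρ(12) = 0.50; ratio √(0.331/0.500) = 0.81

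| Linear decline | ρ̄ | ρ(3) | Ratio, month 3 | Ratio, month 9 | Ratio, month 12 |
|---|---|---|---|---|---|
| 0.70 to 0.60 | 0.656 | 0.682 | 1.04 | 0.96 | 0.93 |
| 0.80 to 0.50 | 0.669 | 0.745 | 1.14 | 0.89 | 0.81 |
| 0.85 to 0.40 | 0.654 | 0.768 | 1.22 | 0.85 | 0.76 |
| Constant | = ρ(3) | – | 1.00 | 1.00 | 1.00 |

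Exponential decline between the same endpoints stays inside these limits (1.04-1.20 at month 3, 0.93-0.79 at month 12).

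**5. Effect on type I error.** At nominal 0.05, the actual rate is 2Φ(−1.96 × ratio): 0.042 to 0.017 at month 3, and 0.069 to 0.136 at month 12.

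**6. Wider assumptions.** A large-sample calculation covered milder decay, steep autoregressive decay and random slopes, with complete data or with assumed retention falling to 50% at month 12, missing completely at random. The 3-month SE was 2-24% too large, the month 9 SE 4-21% too small and the month 12 SE 5-26% too small. Month 6 was closer to correct (ratio 0.90-1.03). With constant correlation 0.6 but unequal visit SDs, the ratio was 1.03-1.08 at month 3 and 0.93-1.05 at month 12.

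**The case against.** Compound symmetry is a legitimate working structure, in effect a random patient intercept, and unequal spacing does not by itself invalidate it. With no correlations in the documents, the standard errors cannot be shown to be wrong. That stands: the size is conditional, and under constant correlation and variance the error is zero.

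The likely error at the key 3-month visit is conservative. The anti-conservative visits are supportive comparisons. The responder analysis and the time-to-deterioration analysis do not use this covariance. All of that stands and limits the consequence.

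A reader might infer more on two counts.

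- *Lost information at 3 months.* A 10% inflated SE looks like a 17% loss (1 − 1/1.1² = 0.17). The data are still used: the compound symmetric point estimate had an SE at most 5% above the efficient estimator at any visit in the cases tried. The cost is power in the reported test.
- *Bias from drop-out.* A likelihood analysis under missing at random does lean on the covariance. In a large-sample check, drop-out that differed by arm gave a bias of about 0.01 SD at month 3 and 0.02-0.03 SD at month 12; the same drop-out rule in both arms gave a negligible one. This is a secondary reason to change.

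Finally, 21 covariance parameters are easy with about 1,200 patients but may not be estimable within small subgroup levels. That stands and shapes the remedy for SAP 3.8.

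**Conclusion.** The point holds as a conditional one. The plan fixes a restrictive covariance, takes intervals from it and includes no check. If correlation falls with time over the range assumed above, with complete data and equal variances, the 3-month SE is about 4-22% too large and the 12-month SE about 7-24% too small, with month 9 in the same direction as month 12.

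The documents do not support saying that the standard errors are wrong, or that this choice puts the key 3-month result at risk of a false positive; its likely effect there is the opposite. Overall survival and the stated power figures are untouched.

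The conservative direction at 3 months concerns the within-patient covariance only. A practice intercept that is constant over time leaves practice-by-time variation out of the SE of a change. That is a separate question: its size is unknown, and it could act the other way.

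**What to change.** In SAP 3.6.3, specify an unstructured within-patient covariance (6 × 7/2 = 21 parameters) and keep the practice random intercept. State the fallback order for non-convergence: heterogeneous Toeplitz, then compound symmetry with robust standard errors clustered by practice. Heterogeneous Toeplitz bands by visit order, not months, so it is a second choice here.

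In SAP 3.8, use the same order and say that the fallback is expected in small subgroup levels.

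SAP 3.5.3 places a SAP update after the analysis of secondary outcomes, and the SAP's summary of changes records a reference to their publication. For outcomes already analysed, report the unstructured model as a labelled sensitivity analysis beside the specified one, showing the month 3, 9 and 12 intervals from both.

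The cost is a short SAP edit and one extra model run, with no new data. The downside is possible non-convergence in small subgroups, which the fallback order covers.
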